2 ETHICAL CONSIDERATIONS

2.1 Good Clinical Practice

This study will be conducted in accordance with Good Clinical Practice (GCP), as defined by the International Conference on Harmonization (ICH) and in accordance with the ethical principles underlying European Union Directive 2001/20/EC and the United States Code of Federal Regulations, Title 21, Part 50 (21CFR50).

The study will be conducted in compliance with the protocol. The protocol and any amendments and the subject informed consent will receive Institutional Review Board/Independent Ethics Committee (IRB/IEC) approval/favorable opinion prior to initiation of the study.

All potential serious breaches must be reported to BMS immediately. A serious breach is a breach of the conditions and principles of GCP in connection with the study or the protocol, which is likely to affect, to a significant degree, the safety or physical or mental integrity of the subjects of the study or the scientific value of the study.

Personnel involved in conducting this study will be qualified by education, training, and experience to perform their respective tasks.

This study will not use the services of study personnel where sanctions have been invoked or where there has been scientific misconduct or fraud (eg, loss of medical licensure, debarment).

2.2 Institutional Review Board/Independent Ethics Committee

Before study initiation, the investigator must have written and dated approval/favorable opinion from the IRB/IEC for the protocol, consent form, subject recruitment materials (eg, advertisements), and any other written information to be provided to subjects. The investigator or BMS should also provide the IRB/IEC with a copy of the Investigator Brochure or product labeling information to be provided to subjects and any updates.

The investigator or BMS should provide the IRB/IEC with reports, updates and other information (eg, expedited safety reports, amendments, and administrative letters) according to regulatory requirements or institution procedures.

2.3 Informed Consent

Investigators must ensure that subjects are clearly and fully informed about the purpose, potential risks, and other critical issues regarding clinical studies in which they volunteer to participate.

In situations where consent cannot be given to subjects, their legally acceptable representatives are clearly and fully informed about the purpose, potential risks, and other critical issues regarding clinical studies in which the subject volunteers to participate.

BMS will provide the investigator with an appropriate (ie, Global or Local) sample informed consent form which will include all elements required by ICH, GCP and applicable regulatory requirements. The sample informed consent form will adhere to the ethical principles that have their origin in the Declaration of Helsinki.

Investigators must:

- 1) Provide a copy of the consent form and written information about the study in the language in which the subject is most proficient prior to clinical study participation. The language must be non-technical and easily understood.
- 2) Allow time necessary for subject or subject's legally acceptable representative to inquire about the details of the study.
- 3) Obtain an informed consent signed and personally dated by the subject or the subject's legally acceptable representative and by the person who conducted the informed consent discussion.
- 4) Obtain the IRB/IEC's written approval/favorable opinion of the written informed consent form and any other information to be provided to the subjects, prior to the beginning of the study, and after any revisions are completed for new information.
- 5) If informed consent is initially given by a subject's legally acceptable representative or legal guardian, and the subject subsequently becomes capable of making and communicating his

or her informed consent during the study, consent must additionally be obtained from the subject.

- 6) Revise the informed consent whenever important new information becomes available that is relevant to the subject's consent. The investigator, or a person designated by the investigator, should fully inform the subject or the subject's legally acceptable representative or legal guardian, of all pertinent aspects of the study and of any new information relevant to the subject's willingness to continue participation in the study. This communication should be documented.

The confidentiality of records that could identify subjects must be protected, respecting the privacy and confidentiality rules applicable to regulatory requirements, the subjects' signed ICF and, in the US, the subjects' signed HIPAA Authorization.

The consent form must also include a statement that BMS and regulatory authorities have direct access to subject records.

The rights, safety, and well-being of the study subjects are the most important considerations and should prevail over interests of science and society.

3 INVESTIGATIONAL PLAN

3.1 Study Design and Duration

This is a Phase 1/2, open-label, multicenter, study of nivolumab, a fully human monoclonal IgG4 antibody targeting the PD-1 membrane receptor on T cells.

NIVOLUMAB/DARATUMUMAB COHORTS

Combination cohorts will evaluate the combination of nivolumab and daratumumab in relapsed/refractory MM patients.

Per Revised Protocol 14, Cohort A is closed to enrollment. Patients who are already on treatment in this cohort will continue to receive study treatment as long as they derive clinical benefit and do not meet the protocol defined criteria for discontinuation ([Section 4.1.5](#)). See [Figure 3.1-1](#).

Cohort B (ND, D) has been added to the study and is open to enrollment. See [Figure 3.1-2](#).

The study will consist of Screening (up to 28 days), Treatment (until disease progression), and Follow-up.

Figure 3.1-1: Study Design for Cohort A (ND ± Pd) Cohort A is closed for enrollment per Revised Protocol 14

[figure not shown]
[figure not shown]

Figure 3.1-2: Study Design for Cohort B (ND and D) Cohort B is open for enrollment per Revised Protocol 14.

* Split dosing is available for Cycle 1 Day 1. See [Section 4.1.1.2](#).

Dosing schematics for the nivolumab/daratumumab cohorts are provided in [Appendix 6](#).

Approximately 60 eligible MM subjects will be enrolled in Cohort B (ND and D) and will be randomized in a 2:1 ratio in favor of the ND regimen. Subjects will continue treatment as long as the subject has clinical benefit from the treatment and does not meet criteria for treatment discontinuation.

All AE data will be monitored on an ongoing basis for safety. Stopping rules for toxicity in the nivolumab-daratumumab arm are specified in [Section 3.1.1.1](#).

For assessment of MRD by molecular and cytometry approaches to detect disease in the bone marrow, all MM subjects will require bone marrow aspirates at the time points described in [Table 5.1-6](#).

Bone marrow and peripheral blood samples are also needed to better understand how the immune microenvironment may contribute to immune evasion, the progression of multiple myeloma, and potential synergies between nivolumab and daratumumab. Bone marrow from every harvest should also be submitted for biomarker analysis, as described in [Table 5.1-6](#). At the time of the scheduled bone marrow aspirate, the PI will determine if there have been significant changes in the clinical course to suggest that subjects can no longer undergo the procedure safely. Similarly, the PI will determine if there have been significant changes in the clinical course to suggest that subjects can no longer safely undergo the additional peripheral blood collection for biomarkers assessments. These subjects may continue therapy.

Clinical response will be assessed based on the modified IMWG criteria based on serum and urine laboratory assessments every 4 weeks from Cycle 1 Day 1 until disease progression,

irrespective of dose delays or treatment interruptions. All response (\geq PR) and progression categories require 2 consecutive laboratory assessments to confirm response or progression before initiation of any new therapy. If progression is confirmed at the second laboratory assessment, all study treatment will be discontinued.

To assess potential daratumumab and nivolumab interference with serum M protein quantification, samples may be analyzed to distinguish daratumumab and nivolumab from endogenous myeloma protein (M protein).

Subjects who experience AEs that require discontinuation of daratumumab may be allowed to continue therapy with nivolumab (if randomized to the ND arm), with or without pomalidomide and dexamethasone, (if randomized to the NDPd arm) if deemed in their best interest by both the PI and the BMS medical monitor. Subjects must be deriving clinical benefit.

Subjects who experience AEs that require discontinuation of nivolumab may be allowed to continue therapy with daratumumab (if randomized to ND arm), with or without pomalidomide and dexamethasone, (if randomized to NDPd arm), if deemed in their best interest by both the PI and the BMS medical monitor. Subjects must be deriving clinical benefit.

Subjects who experience AEs that require discontinuation of nivolumab and daratumumab in the ND-Pd cohort may be allowed to continue therapy with pomalidomide and dexamethasone, if deemed in their best interest by both the PI and the BMS medical monitor. Subjects must be deriving clinical benefit.

Subjects who experience AEs that require discontinuation or delay of pomalidomide in the ND-Pd cohort may be allowed to continue therapy with nivolumab, daratumumab, and dexamethasone, if deemed in their best interest by both the PI and the BMS medical monitor. Subjects must be deriving clinical benefit.

Subjects who experience AEs that require discontinuation or delay of dexamethasone in the ND-Pd cohort may be allowed to continue therapy with nivolumab, daratumumab, and pomalidomide, if deemed in their best interest by both the PI and the BMS medical monitor. Subjects must be deriving clinical benefit.

3.1.1 Stopping Rules

3.1.1.1 Stopping Rules for Toxicity in the ND Arm

The ND arm will be stopped if any of the following safety events are observed:

- Grade \geq 3 nivolumab immune-related adverse events: \geq 10% occurrence in the first 50% of treated patients
- Grade 5 adverse events, excluding those due to disease progression, cumulative rate: \geq 20% occurrence in the first 50% of treated patients.

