3.2 Post Study Access to Therapy

At the conclusion of the study, subjects who continue to demonstrate clinical benefit will be eligible to receive study drug. Study drug will be provided via an extension of the study, a

rollover study requiring approval by responsible health authority and ethics committee or through another mechanism at the discretion of BMS. BMS reserves the right to terminate access to study drug if any of the following occur: a) the marketing application is rejected by responsible health authority; b) the study is terminated due to safety concerns; c) the subject can obtain medication from a government sponsored or private health program; or d) therapeutic alternatives become available in the local market.

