3.5 Discontinuation of Subjects from Treatment

Subjects MUST discontinue investigational product (and noninvestigational product at the discretion of the investigator) for any of the following reasons:

- Withdrawal of informed consent (subject's decision to withdraw for any reason)
- Any clinical AE, abnormal laboratory test results or intercurrent illness which, in the opinion of the investigator, indicates that continued participation in the study is not in the best interest of the subject
- Grade 3 or 4 uveitis related to nivolumab
- Pregnancy
- Termination of the study by BMS
- Loss of ability to freely provide consent through imprisonment or involuntary incarceration for treatment of either a psychiatric or physical (e.g., infectious disease) illness
- Documented and confirmed disease progression or clinical deterioration while receiving active study therapy
- Stopping rules as defined in [Section 3.1.1.1](#).
- Severe nivolumab immune-mediated adverse events, as described in [Appendix 5](#).

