6.1.1 Serious Adverse Event Collection and Reporting

Sections 5.6.1 and 5.6.2 in the nivolumab IB represent the Reference Safety Information to determine expectedness of SAEs for expedited reporting. Following the subject's written consent to participate in the study, all SAEs, whether related or not related to study drug, must be collected, including those thought to be associated with protocol-specified procedures. All SAEs must be collected that occur during the screening period and within 100 days of discontinuation of dosing or within 30 days of the last visit for screen failures. For subjects randomized but never treated with any study drug, SAEs should be collected for 30 days from the date of randomization.

The investigator must report any SAE that occurs after these time periods and that is believed to be related to study drug or protocol-specified procedure.

An SAE report should be completed for any event where doubt exists regarding its seriousness.

If the investigator believes that an SAE is not related to study drug, but is potentially related to the conditions of the study (such as withdrawal of previous therapy or a complication of a study procedure), the relationship should be specified in the narrative section of the SAE Report Form.

SAEs, whether related or not related to study drug, and pregnancies must be reported to BMS (or designee) within 24 hours. SAEs must be recorded on the SAE Report Form; pregnancies on a Pregnancy Surveillance Form (electronic or paper forms). When using paper forms, the reports are to be transmitted via email or confirmed facsimile (fax) transmission to:

SAE Email Address: See Contact Information list.

SAE Facsimile Number: See Contact Information list.

For studies capturing SAEs/pregnancies through electronic data capture (EDC), electronic submission is the required method for reporting. The paper forms should be used and submitted

immediately, only in the event the electronic system is unavailable for transmission. When paper forms are used, the original paper forms are to remain on site.

SAE Telephone Contact (required for SAE and pregnancy reporting): See Contact Information list.

If only limited information is initially available, follow-up reports are required. (Note: Follow-up SAE reports should include the same investigator term[s] initially reported.)

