7 DATA MONITORING COMMITTEE AND OTHER EXTERNAL COMMITTEES

Not applicable.

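### Both ND stopping limits count events only in the first half of treated subjects, so no visible text sets a numeric limit on fatal events in the remaining ND subjects (about 20)

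*Protocol*

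**What the plan says.** Protocol 3.1.1.1 gives two toxicity limits for the ND arm, and meeting either one stops it. Grade 3 or higher nivolumab immune-related events stop it at or above "10% occurrence in the first 50% of treated patients". Grade 5 events not due to progression, described as a cumulative rate, stop it at or above "20% occurrence in the first 50% of treated patients". Protocol 3.5 makes meeting these rules a mandatory reason to discontinue investigational product.

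Elsewhere there is oversight without a number. Protocol 3.1 says "All AE data will be monitored on an ongoing basis for safety. Stopping rules for toxicity in the nivolumab-daratumumab arm are specified in" Section 3.1.1.1, so it points back to the same rule. Protocol 6.1.1 says "SAEs, whether related or not related to study drug, and pregnancies must be reported to BMS (or designee) within 24 hours". Protocol 3.5 also lists "Termination of the study by BMS", and 3.2 foresees that "the study is terminated due to safety concerns". The one scheduled Cohort B interim (8.5.1) falls at 50% of treated patients per arm with three months of follow-up and has no stopping criterion. Other looks (8.5) are made as needed or at a health authority's request. The text under Protocol 7, "DATA MONITORING COMMITTEE AND OTHER EXTERNAL COMMITTEES", is that it does not apply. SAP 2.5 names only a radiology review committee for Hodgkin lymphoma subjects on nivolumab monotherapy.

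**The concern.** The window restricts whose events count. Late deaths among the first half can still count, especially given the word cumulative in the Grade 5 bullet. Deaths among the second half cannot.

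Tolerability of the combination is the primary objective of these cohorts, and the trial is open-label. For about half of the ND subjects, the fatal-event rate that should stop the arm is not fixed in advance. Treatment runs until progression, so a trigger late in enrolment would still protect subjects on drug.

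**Working it through.** **Inputs.** Cohort B has about 60 treated subjects randomized 2:1 (Protocol synopsis; SAP 2.1.2 and 5). The limits are those of Protocol 3.1.1.1. The documents give no expected Grade 5 rate, so 5% to 30% is an assumed range, with outcomes taken as independent between subjects and known at each check.

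**1. The plan's own figures.** The synopsis and SAP 5 give detection probabilities for toxicities, not for the stopping rule. Exact binomial values:
- n = 20: P(X ≤ 1 | 20%) = 6.9% (stated 7%); P(X ≥ 2 | 5%) = 26.4% (stated 26%).
- n = 40: P(X ≤ 3 | 20%) = 2.85% (stated 3%); P(X ≥ 4 | 5%) = 13.8% (stated 14%).

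All four reproduce. The visible text gives no operating characteristics for the stopping rule.

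**2. What the rule covers.** ND subjects: 60 × 2/3 = 40. First half: 20. Grade 5 limit: 0.20 × 20 = 4 events. Immune-related limit: 0.10 × 20 = 2 events. If the window means the first 30 of all 60 Cohort B subjects, 2:1 allocation puts about 20 ND subjects inside it and still leaves about 20 outside.

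**3. Grade 5 limit alone, constant true rate p.** Current rule: P(stop) = P(X ≥ 4 | 20, p). At p = 25% the chance of not firing is P(0) + P(1) + P(2) + P(3) = 0.0032 + 0.0211 + 0.0669 + 0.1339, about 22.5%.

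Extended rule: let q(n, k) be the probability of k events after n subjects with no stop so far. Then q(n, k) = (1 − p) q(n−1, k) + p q(n−1, k−1). At each check, the probability at counts of 20% or more of n is moved to stopped. The limit rises only every five subjects, so checks at 20, 25, 30, 35 and 40 (at least 4, 5, 6, 7 and 8 events) give the same stop probabilities as checking after every subject from 20 on.

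| True rate | Current, ≥4/20 | Extended to 40 | Only ≥6/30 added |
|---|---|---|---|
| 5% | 1.6% | 1.8% | 1.7% |
| 10% | 13.3% | 16.8% | 15.0% |
| 15% | 35.2% | 45.9% | 40.9% |
| 20% | 58.9% | 73.8% | 67.3% |
| 25% | 77.5% | 90.5% | 85.5% |
| 30% | 89.3% | 97.4% | 94.8% |

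The chance of not firing falls from 22.5% to 9.5% at 25% and from 10.7% to 2.6% at 30%. With only the look at 30 added, it is 14.5% and 5.2%. Of the 13.0 points gained at 25%, 9.0 arise at subjects 21 to 30 and 4.0 at subjects 31 to 40.

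**4. Late excess.** Assume 10% in the first 20 subjects and 30% in the second 20. The current rule stops with probability P(X ≥ 4 | 20, 10%) = 13.3%; the extended rule stops with probability 62.1%. The chance that the current rule stays silent while the second half has at least 4 of 20 fatal events is 0.8670 × 0.8929 = 77.4%.

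With only the look at 30 added, sum over x = 0 to 3 the terms P(X = x | 20, 10%) × P(Y ≥ 6 − x | 10, 30%): 0.1216 × 0.0473 + 0.2702 × 0.1503 + 0.2852 × 0.3504 + 0.1901 × 0.6172 = 0.264. Adding 0.133 gives 39.7%.

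**5. Other reading of the current rule.** If the Grade 5 limit is taken to run continuously from subject 10, extending it lowers the chance of not firing from 12.9% to 6.3% at 25% and from 5.8% to 1.7% at 30%.

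**6. Both limits together.** The immune-related limit also stops the arm. At an assumed immune-related rate of 10% it fires with probability P(X ≥ 2 | 20, 10%) = 60.8%, so it stays silent 39.2% of the time. If the two event types are independent and the Grade 5 rate is 25%, the chance that neither limit fires is 0.392 × 22.5% = 8.8% now and 0.392 × 9.5% = 3.7% after extension. At an immune-related rate of 15% (silent 17.6%) these become 4.0% and 1.7%.

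**The case against.** A reader might infer that a late fatal excess could not stop the arm, or that only the sponsor could stop it. The documents do not support either. Cohort A enrolment was itself stopped at FDA request (Protocol document history, Revised Protocol 14). Expedited safety reports go to the IRB/IEC (2.2), suspected unexpected serious reactions go to regulators (6.1.1), and health authorities may request safety updates (8.5). All this stands. What these routes lack is a number.

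A reader might also take the step 3 figures as the chance that the arm continues. They describe the Grade 5 limit alone; step 6 shows that arm-level gains are 5.1 points (8.8% to 3.7%) or 2.3 points (4.0% to 1.7%) under the assumed immune-related rates. Nor do constant-rate figures describe an excess confined to the second half, which is why step 4 is separate.

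Three further points stand in part. Deaths can lag enrolment, so a trigger at subjects 31 to 40 prevents less exposure than an early one. Nothing in the documents makes a 25% to 30% rate of non-progression deaths likely. The trade-off is real: at a true 15%, below the limit, stopping rises by 10.7 points, against 13.0 gained at 25%. How much extra stopping below 20% is acceptable is partly a clinical choice. A reason for the 50% window may also lie in text that is not visible, such as Protocol 8.1. None of this supplies a numeric limit for the second half.

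**Conclusion.** The point holds. Both limits are confined to the first half of treated subjects, and no visible text sets a numeric arm-level limit on non-progression Grade 5 events in the other 20 or so ND subjects. It is a gap in prespecification and not an absence of oversight.

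Under assumed constant rates of 25% or 30%, extending the Grade 5 limit more than halves the chance that it fails to fire if the current rule is a single check at 20. It roughly halves that chance or better if the current rule runs from subject 10. The gap is widest in a late excess such as the one in step 4. These sizes rest on 40 ND subjects, independent outcomes and rates that the documents do not give, and they are smaller for the arm as a whole when the immune-related limit also acts. Confidence is medium.

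**What to change.** Amend the Grade 5 bullet in Protocol 3.1.1.1 so that the 20% limit stays in force for the whole ND arm, counting non-progression Grade 5 events whenever they occur: at least 4 of the first 20 ND subjects, then at least 5 of 25, 6 of 30, 7 of 35 and 8 of 40. At minimum, add one look at 6 or more of 30; step 4 shows that this gives up much of the protection against a late excess.

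The cost is one bullet and four further count checks, with no change to sample size. Against a single check at 20, stopping increases by 0.2 points at a true 5%, 3.5 points at 10% and 10.7 points at 15%.

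Leave the immune-related limit unchanged. Extending it would raise the chance of stopping at a true 5% from 26.4% to 31.7%, a clinical trade-off to be judged separately.

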3.2 Post Study Access to Therapy

At the conclusion of the study, subjects who continue to demonstrate clinical benefit will be eligible to receive study drug. Study drug will be provided via an extension of the study, a

rollover study requiring approval by responsible health authority and ethics committee or through another mechanism at the discretion of BMS. BMS reserves the right to terminate access to study drug if any of the following occur: a) the marketing application is rejected by responsible health authority; b) the study is terminated due to safety concerns; c) the subject can obtain medication from a government sponsored or private health program; or d) therapeutic alternatives become available in the local market.

